#### Scoring of PROs

POEM	Scored according to:
	https://www.nottingham.ac.uk/research/groups/cebd/documents/methodological-
	resources/poem-for-self-completion.pdf
DLQI	Scored according to:
	http://sites.cardiff.ac.uk/dermatology/quality-of-life/dermatology-quality-of-life-
	index-dlqi/dlqi-instructions-for-use-and-scoring/
EQ-5D-	Index values calculated according to:
5L	https://euroqol.org/eq-5d-instruments/eq-5d-51-about/valuation-standard-value-
	sets/crosswalk-index-value-calculator/
	The UK value sets will be used.
HADS	The HADS consists of 14 items, 7 of which are related to anxiety and 7 related
	to depression. The maximum score is 21 for each subscale (anxiety and
	depression).
	If one question is missing within a subscale, the response to that question will
	be imputed as the mean of the remaining questions in that subscale. If more than
	one question is missing within a subscale, the subscale is considered missing.
SF-36	Scored by QualityMetric Health Outcomes(tm) Scoring Software 5.0 Q provided
	with license.
WPAI-	Scored according to:
GH	http://www.reillyassociates.net/WPAI_Scoring.html
TSQM	Scored according to User Manual for the Treatment Satisfaction Questionnaire
v.II	for Medication (TSQM) 1.0 provided with license.

#### PROs in the open-label period

By mistake PROs are reported in some instances for subjects in the open-label period. These data will be presented in listings only.

#### Missing baseline assessments

When the baseline value is missing, endpoints concerning a change from baseline will not be derived, and such subjects will be excluded from the analysis. Since the missingness of baseline values are unrelated to the assigned treatment, bias should not be a concern with this approach.

# 6.7 Analysis of Safety

#### 6.7.1 Adverse Events

Adverse events will be summarised and listed.

#### Assignment of AEs to periods

An adverse event will be assigned to a given period (initial, maintenance, open-label or follow-up) if the start date is after the start date and before the end date of that period (see Section 6.8.2, Table 4).

For AEs with start day on the same day as the first dose was given, only AEs starting after the first dose was given will be considered treatment emergent and assigned to the initial treatment period.

AEs with start date on the same day as the first dose of maintenance treatment will be assigned to the initial or maintenance period depending on whether the AE started before or after the dose was given.

AEs with start date on the same day as the first dose of open-label treatment will be assigned to the previous treatment period (can be initial or maintenance) or assigned to the open-label period depending on whether the AE started before or after the dose was given.

AEs starting on the day of exposure end (as defined in Section 6.8.2) will be assigned to the last treatment period.

For handling of incomplete start dates of adverse events, see Section 6.8.3.

#### Sort order of AE tables

Generally, AE tables by system organ class and/or preferred term will be sorted by decreasing number of affected subjects:

- For the initial treatment period, AE tables will be sorted by decreasing number of affected subjects in the Tralokinumab Q2W group.
- For the maintenance treatment period, AE tables will be sorted by decreasing total number of affected subjects in the Tralokinumab treatment groups (sum of Q2W and Q4W).
- For the entire treatment period, AE tables will be sorted by decreasing number of affected subjects in the "Tralokinumab total" group.

• For the follow-up period, AE tables will be sorted by decreasing total number of affected subjects in the Tralokinumab treatment groups (sum of Q2W, Q4W and Q2W+optional TCS).

# 6.7.2 Vital signs

Vital signs will be summarised and listed.

For the summary tables of vital signs by visit, the last pre-dose vital sign assessment will be presented. If no dosing occurs at a visit, the last assessment recorded at the visit will be presented. For the first 3 IMP dosing visits in both the initial and open-label treatment period, subjects will be monitored after IMP administration for immediate drug reactions for a minimum of 2 hours with vital signs taken every 30 minutes or until stable, these measurements will only be listed.

# 6.7.3 ECG

ECG data will be summarised and listed. The overall central evaluation of ECG will be presented using shift tables.

# 6.7.4 Laboratory Data

Laboratory data will be summarised and listed.

For the laboratory values, if the value is below the lower limit of quantification, half of the lower limit will be used for quantitative summaries. If the value if above the upper limit of quantification, the upper limit value will be used.

If more than one laboratory value is reported for the same visit, the latest value will be used in summary statistics and analyses.

Potentially clinically significant values will be defined as displayed in Table 2.

Protocol Lab parameter	SI Unit	PCS low	PCS High
Biochemistry			
Sodium	mmol/L	< 129 mmol/L, < 125 mmol/L	> 160 mmol/L
Potassium	mmol/L	< 3 mmol/L, < 2.5 mmol/L	> 6.5 mmol/L, > 7.5 mmol/L

Table 2: Potentially clinically significant biochemistry and haematology values

Trial ID: LP0162-1325	Date: 20-May-2019	Version: 1.0
		Page 24 of 31

Creatinine	umol/L	N/A	> 1.5 xULN, > 3 xULN
Calcium	mmol/L	< 1.9 mmol/L	> 3.0 mmol/L,
			> 3.5 mmol/L
Alkaline phosphatase	U/L	N/A	> 3xULN
Aspartate	U/L	N/A	> 3xULN, $> 5$ xULN,
aminotransferase			> 10 xULN, > 20 xULN
Alanine aminotransferase	U/L	N/A	> 3xULN, $> 5$ xULN,
			> 10 xULN, > 20 xULN
Bilirubin	umol/L	N/A	>2xULN
Cholesterol	mmol/L	N/A	> 6.2 mmol/L
LDL cholesterol	mmol/L	N/A	> 4.1 mmol/L,
			> 4.9 mmol/L
HDL cholesterol	mmol/L	N/A	> 1.6 mmol/L
Triglycerides	mmol/L	N/A	> 2.3 mmol/L,
			> 5.6 mmol/L
Glucose (non-fasting)	mmol/L	< 3.9 mmol/L	>11.1 mmol/L
Haematology			
Haemoglobin	g/L	<110 g/L, < 80 g/L	> 185 g/L for male,
-	-		> 165 g/L for female
Neutrophils, absolute	10  /L	$< 1.5 \ 10^{9}/L, < 1.0 \ 10^{9}/L,$	N/A
count		< 0.5 10  /L	
Lymphocytes, absolute	$10^{9}/L$	$< 1.0 \text{ x } 10^9 / \text{L},$	$> 5.0 \text{ x } 10^9/\text{L}$
count		$< 0.5 \text{ x } 10^9/\text{L}$	
Monocytes, absolute count	$10^{9}/L$	$< 0.1 \text{ x } 10^9/\text{L}$	$> 0.8 \text{ x } 10^9/\text{L}$
Eosinophils, absolute	$10^{9}/L$	N/A	> 1.5, > 5.0
count			
Basophils, absolute count	$10^{9}/L$	N/A	> 0.2
Thrombocytes	10  /L	$< 100 \text{ x } 10^9 \text{/L},$	$>450 \text{ x } 10^9/\text{L}$
-		$< 30 \text{ x } 10^9/\text{L},$	
	• • • • •	$< 10 \times 10^{9}/L$	1

PCS: potentially clinically significant; ULN: Upper limit of normal, i.e. upper limit of normal reference range.

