The investigator must evaluate all results outside the reference range ('clinically significant' or 'not clinically significant') and sign and date. The signed and dated version will be filed with the investigator's trial documentation. Clinically significant abnormal tests must be repeated to confirm the abnormality.

Trial ID: LP0162-1325	Date: 14-Aug-2018	Version: 4.0
		Page 78 of 169

The central laboratory will provide results in conventional units to trial sites in the US and in SI units to trial sites in Europe and Asia; results that are transferred to the trial database will be in conventional and SI units.

Handling, storage, destruction and shipment instructions are provided in a separate laboratory manual.

If a screening laboratory result is abnormal and of clinical significance, it will be at the investigator's discretion to decide if the subject should be enrolled into the trial (respecting exclusion criteria no. 26, 27, and 28).

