12.3.7.3 Clinical laboratory evaluation

The change in each of the laboratory parameters from baseline to each visit will be summarised by visit and treatment group as mean, standard deviation, median, minimum and maximum values for the safety analysis set, the maintenance safety analysis set, and the open-label safety analysis set.

Laboratory parameters will be classified as 'low', 'normal' or 'high', depending on whether the value is below, within or above the reference range, respectively. A shift table will be produced showing the categories at baseline against those at end of treatment. Subjects with laboratory parameters outside the reference range will be listed.

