Appendix 2: Definitions of adverse events and serious adverse events

Adverse event definition

An AE is defined as any untoward medical occurrence in a patient or clinical investigation subject administered a pharmaceutical product and which does not necessarily have a causal relationship with this treatment. An AE can therefore be any unfavourable and unintended sign (including an abnormal laboratory finding), symptom, or disease temporally associated with the use of a medicinal (investigational) product, whether or not related to the medicinal (investigational) product. (ICH Harmonized Tripartite Guideline for Good Clinical Practice, E6 (R1)).

This definition includes:

 accidental injuries, events related to trial procedures, reasons for any unfavourable and unplanned change in medication (drug and/or dose), clinically significant worsening of pre-existing conditions, or reasons for admission to hospital or surgical procedures unless these were planned before enrolment. It also includes AEs commonly observed and AEs anticipated based on the pharmacological effect of the IMP. In addition, any laboratory abnormality assessed as clinically significant by the investigator must be recorded as an AE.

Serious adverse event definition

An SAE is any untoward medical occurrence that

- results in death.
- is life-threatening.
- requires inpatient hospitalisation or prolongation of existing hospitalisation. Planned hospitalisation or planned prolonged hospitalisation do not fulfill the criteria for being an SAE but should be documented in the subject's medical record.
- results in persistent or significant disability/incapacity.
- is a congenital anomaly/birth defect.

or

• is a medically important condition. Events that may not be immediately lifethreatening or result in death or hospitalisation but may jeopardise the subject or may require intervention to prevent one of the other outcomes listed in the definition above. Examples are intensive treatment in an emergency room or at home for allergic bronchospasm, blood dyscrasias and convulsions that do not result in hospitalization, development of drug dependency or drug abuse.

Trial ID: LP0162-1325	Date: 14-Aug-2018	Version: 4.0
		Page 126 of 169

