# 6.8.6 Early termination and unscheduled visits

When no data is available from a certain scheduled post-baseline visit for a particular subject, data from early termination visits and unscheduled visits have the potential to replace data from that particular scheduled visit in data summaries, provided the data is collected between 6 days before and 7 days after the planned time point for the scheduled visit, as displayed below.

Visit (Target day)	Visit window (Day is date of assessment
	minus date of first dose)
Week 2 (Day 14)	Day 8 to 21
Week x (Day $7*x$ ) (where $x=4, 6,, 52$ )	Day 7*x-6 to 7*x+7
Week x (Day 7*x) (where x=54, 56,, 68)	Day 7*x-6 to 7*x+7
(only applicable for subjects enrolled in	
short-term extension)	
Safety follow-up	106-119 days after last dose

When both unscheduled and early termination visits exist within the given visit window, the early termination visit will be selected for analysis. When no early termination visits and several unscheduled visits exist, the unscheduled visit closest to the target day will be selected for analysis. If the difference is a tie, the latest unscheduled visit will be selected.

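### Taking the latest laboratory value per visit can drop a threshold-crossing result from the safety counts when its retest carries the same visit label

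*SAP*

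**What the plan says.** SAP 6.7.4 has one rule for several results at one visit: "If more than one laboratory value is reported for the same visit, the latest value will be used in summary statistics and analyses". The rule itself expects more than one value under a single visit label, and it makes no exception for any type of table. The same section goes on: "Potentially clinically significant values will be defined as displayed in Table 2". It does not say whether values are judged against those thresholds by visit, at any time, or at their worst.

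Protocol 10.4.5 sets the trigger for a repeat. First, "The investigator must evaluate all results outside the reference range ('clinically significant' or 'not clinically significant') and sign and date". Then, "Clinically significant abnormal tests must be repeated to confirm the abnormality". No other laboratory result has a mandated repeat.

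Protocol 12.3.7.3 plans change from baseline by visit, a low/normal/high shift table ("A shift table will be produced showing the categories at baseline against those at end of treatment") and a listing ("Subjects with laboratory parameters outside the reference range will be listed"). Protocol Appendix 2 adds that "any laboratory abnormality assessed as clinically significant by the investigator must be recorded as an AE".

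SAP 6.8.6 lets unscheduled or early termination data stand in for a scheduled visit in data summaries under one condition: "When no data is available from a certain scheduled post-baseline visit for a particular subject". Neither document says under which visit a retest is filed.

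**The concern.** Each rule is ordinary alone; together they select in one direction. A mandated second value exists only because the first was abnormal, and the latest-value rule then keeps the second. An abnormal result with a normal retest becomes normal. A normal first result has no mandated retest that could turn it abnormal.

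At stake are the counts of subjects crossing the limits in SAP Table 2, by treatment group. These counts depend on isolated extreme results, and those are the results most likely to be retested.

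**Working it through.** The documents give no retest rate, laboratory variance or expected PCS rate, so there is no planned figure to reproduce. The check has a reading of the rules and an illustration on stated assumptions.

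**Reading the rules together**

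| Where the retest or finding is filed | Rule that applies | Effect on PCS counts |
|---|---|---|
| Retest under the same visit, normal | SAP 6.7.4, latest value | First value drops out |
| Retest under the same visit, confirms | SAP 6.7.4, latest value | Nothing lost |
| Retest as an unscheduled visit | SAP 6.8.6, scheduled value exists | First value kept |
| Abnormality found only at an unscheduled visit | SAP 6.8.6, scheduled value exists | Left out of by-visit summaries |

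The shift table compares baseline with end of treatment, so on the post-baseline side only a retest at the end-of-treatment visit can change a subject's category.

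**Illustration of size**

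Assume the first result X1 and retest X2 are standard bivariate normal with correlation ρ, and the flag is a one-sided cut-off c. Let q be the share of flagged first values that are retested under the same visit label.

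- Confirmation probability: r = P(X1 > c and X2 > c) / P(X1 > c)
- Retained share of first exceedances: K = 1 − q(1 − r)

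For a cut-off exceeded by 1% of results, c = 2.326. In the 585 tralokinumab subjects of Protocol 12.1, 585 × 0.01 = 5.85 exceed it at one visit.

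| ρ | joint probability | r (= K at q = 1) | subjects kept, q = 1 | K at q = 0.5 | K at q = 0 |
|---|---|---|---|---|---|
| 0.5 | 0.00129 | 0.129 | 5.85 × 0.129 = 0.8 | 0.565 | 1 |
| 0.7 | 0.00267 | 0.267 | 5.85 × 0.267 = 1.6 | 0.633 | 1 |
| 0.9 | 0.00542 | 0.542 | 5.85 × 0.542 = 3.2 | 0.771 | 1 |

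At q = 1, a 5% cut-off keeps 0.244, 0.392 and 0.637 for the same correlations; a 0.2% cut-off keeps 0.070, 0.186 and 0.468. Over this grid the loss runs from 36% (1 − 0.637) to 93% (1 − 0.070).

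A simulation of 4 million pairs (1% cut-off, ρ = 0.7, q = 1) gave exceedance rates of 1.01% on first values, 0.27% on latest values and 1.01% on worst values. The overall mean moved by −0.008 SD.

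**Effect on the comparison between arms**

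Add an assumed 0.3 SD upward shift in one arm, with q = 1. The latest value exceeds the flag only if both results do.

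| ρ, flag | First value: difference, ratio | Latest value: difference, ratio |
|---|---|---|
| 0.8, 2 SD | 4.46% − 2.28% = 2.18 points, 1.96 | 2.16% − 0.98% = 1.18 points, 2.20 |
| 0.6, 2.5 SD | 1.39% − 0.62% = 0.77 points, 2.24 | 0.289% − 0.101% = 0.19 points, 2.86 |
| 0.4, 3 SD | 0.347% − 0.135% = 0.21 points, 2.57 | 0.0182% − 0.0046% = 0.014 points, 3.99 |

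The absolute difference shrinks and the ratio grows. The table that results has far fewer events in it.

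**The case against.** The strongest objection is that replacement needs a shared visit label, which the documents leave open. Chemistry and haematology go to a central laboratory, and the investigator reviews the returned result. A fresh sample could well be filed as an unscheduled visit or fall at the next scheduled one. SAP 6.8.6 then keeps the first value and nothing is lost. This stands, and it is why the size starts at zero. It does not remove the point, because SAP 6.7.4 is written for cases where values do share a visit.

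Second, there are other routes. Results judged clinically significant are recorded as adverse events, and Protocol 12.3.7.1 tabulates these by treatment group and compares the percentages in the initial period. Out-of-range subjects are listed, and the data monitoring committee sees specific laboratory parameters (Appendix 4H). This also stands: the results are not hidden. Adverse event records follow the investigator's judgement, however, and do not restore a count against the Table 2 limits.

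Third, the correlations and cut-offs are not trial data, and Table 2 uses clinical limits, not SD units. Agreed; they show a range only.

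A reader might infer more than the documents support:

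- That all abnormal tests are repeated. The mandate covers only those judged clinically significant. Discretionary repeats are not ruled out, so a normal value could also be replaced.
- That the laboratory tables as a whole are biased. By-visit means barely move, and retests at intermediate visits do not enter the end-of-treatment column of the shift table.
- That a real difference between arms is always diluted. This holds for the absolute difference but not for the risk ratio.

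**Conclusion.** The point holds for the PCS counts, and for the shift table at end of treatment only. The latest-value rule and the selective repeat mandate can together remove true first exceedances, and the SAP has no worst-value rule to protect them. Separately, SAP 6.8.6 leaves abnormalities found only at unscheduled visits out of by-visit summaries when a scheduled value exists.

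The size is unknown. With no shared labels there is no replacement loss. With all labels shared and a correlation of 0.7 or below, more than 60% of single-visit exceedances go at each cut-off examined. This rests on the bivariate normal model and on q, which combines how often a flagged value is retested with how the retest is filed. Listings and adverse event records limit the consequence. This is a cheap improvement to a safety table; it gives no ground to doubt the laboratory safety evaluation as a whole.

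**What to change.** In SAP 6.7.4:

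1. Base PCS tables on the worst post-baseline value within each treatment period, including repeat and unscheduled samples.
2. Limit the one-value-per-visit rule to by-visit summaries, and use the first valid scheduled sample there.
3. Keep the baseline-to-end-of-treatment shift table of Protocol 12.3.7.3, using the first valid scheduled end-of-treatment sample and not its retest. Taking the most extreme value of the period for this table would conflict with the protocol and is not proposed.
4. State under which visit a retest is filed.

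The cost is a short text change and one derived flag in the laboratory dataset. The downside is that some spurious single abnormalities will be counted in the PCS tables; the listings can show the retest beside each of them.

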10.4.5 Laboratory testing

The following safety samples will be analysed by a central laboratory: chemistry, haematology, serology, and serum pregnancy (Panel 13). Urine samples will be tested at the trial site with a dipstick; if abnormal, a urine sample will be sent to the central laboratory for further analysis.

A laboratory manual will be provided to the sites that specifies the procedures for collection, processing, storage, and shipment of samples, as well as laboratory contact information specific to this trial.

Samples for laboratory testing will be collected according to the SoP (Section 4).

Panel 13 Central laboratory testing	Panel 13	Central	laboratory	testing
-------------------------------------	----------	---------	------------	---------

Chemistry	Haematology
Sodium	Erythrocytes
Potassium	Hematocrit
Creatinine	Hemoglobin
Urea nitrogen	Erythrocyte mean corpuscular volume
Calcium	Erythrocyte mean corpuscular haemoglobin
Alkaline phosphatase	concentration
Aspartate aminotransferase	Leukocytes
Alanine aminotransferase	Neutrophils, neutrophils/total cells
Gamma glutamyl transferase	Lymphocytes, lymphocytes/total cells
Bilirubin ¹	Monocytes, monocytes/total cells
Lactate dehydrogenase	Eosinophils, eosinophils/total cells
Cholesterol	Basophils, basophils/total cells
LDL cholesterol	Thrombocytes
HDL cholesterol	Serology
Triglycerides	Hepatitis B virus surface antigen ⁴
Glucose (non-fasting)	Hepatitis B virus surface antibody ⁴
Albumin	Hepatitis B virus core antibody ⁴
Protein	Hepatitis C virus antibody ⁴
Tryptase ²	HIV-1 antibody ⁴
	HIV-2 antibody ⁴
	Immunoglobulin E ⁵
Urinalysis ³	Serum pregnancy test (females only) ⁴
Protein	Choriogonadotropin beta
Glucose	
Ketones	
Occult blood	
Leukocytes	
Nitrite	

1) If bilirubin is above upper limit of normal, direct and indirect bilirubin will also be measured.

2) Only measured in case of suspected anaphylaxis (Section 9.2).

 Urine samples will be tested at the trial site (dipstick). In case of abnormal dipstick results, a urine sample will be sent to the central laboratory for microscopic examination (leukocytes, erythrocytes, and casts).

Measured at screening only.

5) Not measured at screening.

HDL, high density lipoprotein; LDL, low density lipoprotein.

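### SAP Table 2 sets a potentially clinically significant limit for HDL cholesterol on the high side only, so the flag cannot pick out low HDL and marks generally favourable values instead

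*SAP*

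**What the plan says.** HDL is a planned safety parameter: "HDL cholesterol" is listed under chemistry in Panel 13 of Protocol 10.4.5.

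SAP 6.7.4 makes Table 2 the sole definition of a PCS biochemistry or haematology value: "Potentially clinically significant values will be defined as displayed in Table 2". The column headings are "Protocol Lab parameter SI Unit PCS low PCS High", and the HDL entry is "HDL cholesterol mmol/L N/A > 1.6 mmol/L". Read against the headings, the low limit is N/A and the high limit is 1.6 mmol/L.

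The neighbouring lipid rows have the same layout: "Cholesterol mmol/L N/A > 6.2 mmol/L" for total cholesterol, and "LDL cholesterol mmol/L N/A > 4.1 mmol/L" for LDL, with a second step at 4.9 mmol/L. Triglycerides are also high-only. Other rows do carry low limits, for example "Glucose (non-fasting) mmol/L < 3.9 mmol/L >11.1 mmol/L".

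Table 2 is not the only laboratory output. Protocol 12.3.7.3 covers every parameter: "The change in each of the laboratory parameters from baseline to each visit will be summarised by visit and treatment group as mean" and other descriptive statistics. It also classifies values against the reference range, cross-tabulates those categories at baseline and end of treatment, and lists subjects outside the range. SAP section 4 keeps the protocol's analyses in force.

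**The concern.** A PCS limit is meant to separate values that deserve clinical attention from ordinary variation. For total cholesterol, LDL and triglycerides the worrying direction is upward, and Table 2 flags upward. For HDL the worrying direction is generally taken to be downward, yet Table 2 treats it like the other lipids.

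Two things follow. No low HDL, however extreme, can be marked as PCS. And subjects above 1.6 mmol/L, a level generally regarded as favourable, are marked as having a potential problem. A reader who relies on the PCS display for HDL would be looking at the wrong subjects.

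**Working it through.** No figure in the plan needs reproducing, because the question is the direction of a rule. I checked it by reading the table and following the rule through.

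**1. Is the row read correctly?** The four headings (parameter, unit, low limit, high limit) match the four entries of the HDL row. The row is intact, and a broken extraction does not explain the position of N/A.

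**2. Does N/A carry meaning in this table?** Yes. Table 2 is direction-specific throughout:

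| Parameter | Low limit | High limit |
|---|---|---|
| Neutrophils | yes (three steps) | N/A |
| Creatinine, AST, ALT | N/A | yes |
| Potassium, glucose, haemoglobin | yes | yes |
| Total cholesterol, LDL, triglycerides | N/A | yes |
| HDL | N/A | yes |

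In the first four lines N/A is a plausible choice of a side that is not of interest. For HDL it falls on the side generally regarded as adverse. Because HDL shares the layout of the other lipids, the pattern may simply have been carried over; that is an inference.

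**3. What does the rule do?** A value is flagged if and only if HDL > 1.6 mmol/L. Hence:
- no low value can be flagged;
- the flag depends on level, not change, so a fall that ends above 1.6 mmol/L is still flagged, as high;
- a fall that ends at or below 1.6 mmol/L gives no flag.

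**4. Where else would low or falling HDL appear?**
- A value below the reference range is classed as low and the subject is listed (Protocol 12.3.7.3).
- If the value is low at end of treatment, it also enters the shift table. A low value only at an intermediate visit does not, because the table compares baseline with end of treatment.
- A fall within the reference range contributes to the mean change by visit and treatment group.
- Investigators must judge every out-of-range result for clinical significance (Protocol 10.4.5), and a clinically significant abnormality is recorded as an adverse event (Appendices 2 and 4D).

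**5. Can the number of flags be computed?** The proportion above the limit would be 1 − Φ((1.6 − μ)/σ), if HDL were normal with mean μ and standard deviation σ. The documents supply only the 1.6. As a pure assumption, take σ = 0.4 mmol/L:
- μ = 1.2: 1 − Φ(1.0) = 16%
- μ = 1.4: 1 − Φ(0.5) = 31%
- μ = 1.6: 1 − Φ(0) = 50%

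The spread shows how completely the answer depends on the assumed mean. I carry no count forward.

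**The case against.** The strongest reply is that nothing is lost. Low and falling HDL are covered by the group summaries, the shift table, the listing, investigator review and adverse event reporting. A PCS-low limit set at the lower reference limit would repeat the low category that Protocol 12.3.7.3 already produces. Lipid effects are not among the potential risks named in Protocol 5.5 or the adverse events of special interest in Panel 14. And neither document says which direction of HDL is adverse.

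Most of this stands, and it is why the point is minor. It does not dispose of the point. None of the other outputs removes the high-side flag, which would still label generally favourable values as potentially significant. The overlap with the reference-range category is real, but it does not justify leaving the PCS row pointing the other way.

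Two stronger readings are tempting, and the documents do not support them:

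- **That the safety tables miss every subject whose HDL falls.** The PCS flag measures level, not change; a fall that ends above 1.6 mmol/L is still flagged; and the outputs in Protocol 12.3.7.3 show low values and mean falls.
- **That a treatment-related fall would be reported as a safety advantage.** A downward shift could reduce the number of HDL flags, but the SAP specifies no comparison of PCS counts between arms, and the mean change by treatment group would show the fall directly.

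A count of false flags per visit is likewise unsupported. It needs an HDL distribution that the documents do not give, and the SAP does not say that PCS values are tabulated by visit.

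**Conclusion.** The HDL row is wrong as written, or at least unexplained: the PCS criterion cannot identify low HDL and flags values on the side generally regarded as favourable. That the row has this effect follows from the SAP alone. That it is the wrong effect rests on one assumption from general clinical knowledge, namely that low HDL is the adverse direction.

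The consequence is confined to a descriptive PCS safety output. No efficacy endpoint, significance level or power figure is affected, and other planned laboratory outputs still show low or falling HDL. The number of subjects affected is not known. Minor.

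**What to change.** In SAP Table 2, change the HDL high limit to N/A and define the low limit relative to the central laboratory's lower reference limit, using sex-specific limits if the laboratory's range has them. Both devices already occur in the table: creatinine and the transaminases are tied to the upper reference limit, and the haemoglobin high limit differs by sex. Alternatively, keep the row and state why a high HDL is the direction of interest.

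The cost is one table row and its programming. HDL is already measured centrally, so no new data are needed. Protocol 12.3.10 allows changes to the planned analysis to be described and justified in a SAP update or in the clinical trial report, so the correction has a ready place.
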